19.2 Appendix 2: DAS28-hsCRP formula

As per CTP Section 7.3.1.3, the DAS28-hsCRP will be computed according to below formula:

$$\text{DAS28-hsCRP} = 0.56 * \sqrt{(\text{TJC28})} + 0.28 * \sqrt{(\text{SJC28})} + 0.014 * \text{GH} + 0.36 * \ln(\text{hsCRP} + 1) + 0.96$$

Where,

- TJC28=28 Tender Joint Counts (14 joints on each side of the subject's body: 2 shoulders, 2 elbows, 2 wrists, 10 metacarpophalangeal joints, 2 interphalangeal joints of the thumb, 8 proximal interphalangeal joints, and 2 knees)
- SJC28=28 Swollen Joint Counts (same joints used as for TJC28)
- $\ln(\text{hsCRP})$ =natural logarithm of hsCRP
- GH=the General Health component of the DAS (ie Subject's Global Assessment of Disease Activity).

19.3 Appendix 3: Important Protocol Deviations identified by programming and Clinically Important Protocol Deviations

Protocol Deviation number	Protocol Deviation	Important	Clinically Important	Type criteria	Inclusion/Exclusion criteria number	Check
PDEV01	Age < 18 or > 75 at trial entry	Yes	Yes	Eligibility and Entry Criteria	Inclusion criteria #1	If calculated age at informed consent is <18 or >75 years, or if corresponding inclusion criterion is ticked No.
PDEV02	No diagnosis of RA > 6 months' duration at Screening	Yes	Yes	Eligibility and Entry Criteria	Inclusion criteria #2	If no diagnosis of RA or time between diagnosis of RA and Screening Visit is less than 6 months or corresponding inclusion criterion is ticked No.
PDEV03	Negative RF and negative anti-CCP	Yes	Yes	Eligibility and Entry Criteria	Inclusion criteria #3	If RF (IgG-RF, IgM-RF, IgA-RF) is classified as negative (\leq ULN) and Anti-CCP classified as negative (\leq ULN) at the Screening visit or corresponding inclusion criterion is ticked No.
PDEV04	Absence of persistently active disease	Yes	Yes	Eligibility and Entry Criteria	Inclusion criteria #4	If subject has less than 6 swollen joints (of 66 counted) or less than 6 tender joints (of 68 counted) at Screening Visit or corresponding inclusion criterion is ticked No.

Protocol Deviation number	Protocol Deviation	Important	Clinically Important	Type criteria	Inclusion/Exclusion criteria number	Check
PDEV05	hsCRP < 3.6 mg/L	Yes	Yes	Eligibility and Entry Criteria	Inclusion criteria #5	If hsCRP < 3.6 mg/L at Screening Visit or corresponding inclusion criterion is ticked No.
PDEV06	Treatment for less than 12 weeks with 10 to 25 mg/week MTX	Yes	Yes	Eligibility and Entry Criteria	Inclusion criteria #6	If no relevant previous medication is reported in the eCRF as MTX, or a relevant medication reported with a duration less than 12 weeks or a dose not included between 10 and 25 mg, or corresponding inclusion criterion is ticked No.
PDEV07	Women of childbearing potential do not agree to use highly effective methods of contraception	Yes	Yes	Eligibility and Entry Criteria	Inclusion criteria #7	If corresponding inclusion criterion is ticked No.
PDEV08	Males do not agree to use or to have their female partners use highly effective contraception	Yes	Yes	Eligibility and Entry Criteria	Inclusion criteria #8	If corresponding inclusion criterion is ticked No.

Protocol Deviation number	Protocol Deviation	Important	Clinically Important	Type criteria	Inclusion/Exclusion criteria number	Check
PDEV09	Women of childbearing potential do not have negative serum pregnancy test at screening or negative urine pregnancy test at Day 1	Yes	Yes	Eligibility and Entry Criteria	Inclusion criteria #9	If women have a positive serum pregnancy test at Screening visit or a positive urine pregnancy test at Day 1 before randomization and dosing, or corresponding inclusion criterion is ticked No.
PDEV10	History of vaccination not compliant	Yes	Yes	Eligibility and Entry Criteria	Inclusion criteria #10	If identified by medical review or corresponding inclusion criterion is ticked No.
PDEV11	Informed consent not signed	Yes	Yes	Eligibility and Entry Criteria	Inclusion criteria #11	If missing date of informed consent, or corresponding inclusion criterion is ticked No.
PDEV12	Use or change in dose of corticosteroids	Yes	Yes	Eligibility and Entry Criteria	Exclusion criteria #1	If identified by medical review or corresponding exclusion criterion is ticked Yes.
PDEV13	Initiation or change in dose for nonsteroidal anti-inflammatory drugs	Yes	Yes	Eligibility and Entry Criteria	Exclusion criteria #2	If identified by medical review or corresponding exclusion criterion is ticked Yes.
PDEV14	Treatment with tofacitinib, other BTK inhibitors, or a biologic DMARD, or other immunosuppressive drugs other than MTX	Yes	Yes	Eligibility and Entry Criteria	Exclusion criteria #3	If identified by medical review or corresponding exclusion criterion is ticked Yes.

Protocol Deviation number	Protocol Deviation	Important	Clinically Important	Type criteria	Inclusion/Exclusion criteria number	Check
PDEV15	Treatment with anti-CD20 therapy (eg, rituximab)	Yes	Yes	Eligibility and Entry Criteria	Exclusion criteria #4	If identified by medical review or corresponding exclusion criterion is ticked Yes.
PDEV16	Immunologic disorder other than RA	Yes	Yes	Eligibility and Entry Criteria	Exclusion criteria #5	If identified by medical review or corresponding exclusion criterion is ticked Yes.
PDEV17	Vaccination with live or live attenuated virus vaccine	Yes	Yes	Eligibility and Entry Criteria	Exclusion criteria #6	If identified by medical review or corresponding exclusion criterion is ticked Yes.
PDEV18	Severe drug allergy or history of anaphylaxis	Yes	Yes	Eligibility and Entry Criteria	Exclusion criteria #7	If identified by medical review or corresponding exclusion criterion is ticked Yes.
PDEV19	Significant viral, bacterial or fungal infection	Yes	Yes	Eligibility and Entry Criteria	Exclusion criteria #8	If identified by medical review or corresponding exclusion criterion is ticked Yes.
PDEV20	History of or positive HIV, hepatitis C, hepatitis B and/or IgM antibody	Yes	Yes	Eligibility and Entry Criteria	Exclusion criteria #9	If identified by medical review or corresponding exclusion criterion is ticked Yes.
PDEV21	History of or current diagnosis of active TB	Yes	Yes	Eligibility and Entry Criteria	Exclusion criteria #10	If identified by medical review or corresponding exclusion criterion is ticked Yes.
PDEV22	History of splenectomy or any major surgery	Yes	Yes	Eligibility and Entry Criteria	Exclusion criteria #11	If identified by medical review or corresponding exclusion criterion is ticked Yes.

Protocol Deviation number	Protocol Deviation	Important	Clinically Important	Type criteria	Inclusion/Exclusion criteria number	Check
PDEV23	History of any myocardial infarction or cerebrovascular event	Yes	Yes	Eligibility and Entry Criteria	Exclusion criteria #12	If identified by medical review or corresponding exclusion criterion is ticked Yes.
PDEV24	Anticoagulation or antiplatelet therapy other than daily aspirin for cardioprotection	Yes	Yes	Eligibility and Entry Criteria	Exclusion criteria #13	If identified by medical review or corresponding exclusion criterion is ticked Yes.
PDEV25	Fish oil	Yes	Yes	Eligibility and Entry Criteria	Exclusion criteria #14	If identified by medical review or corresponding exclusion criterion is ticked Yes.
PDEV26	History of cancer unless considered cured > 5 years	Yes	Yes	Eligibility and Entry Criteria	Exclusion criteria #15	If identified by medical review or corresponding exclusion criterion is ticked Yes.
PDEV27	Breastfeeding/lactating or pregnant women	Yes	Yes	Eligibility and Entry Criteria	Exclusion criteria #16	If identified by medical review or corresponding exclusion criterion is ticked Yes.
PDEV28	Clinically significant abnormality on ECG or an active infective process or any other clinically significant abnormality on CXR, per Investigator opinion	Yes	Yes	Eligibility and Entry Criteria	Exclusion criteria #17	If identified by medical review or corresponding exclusion criterion is ticked Yes.

Protocol Deviation number	Protocol Deviation	Important	Clinically Important	Type criteria	Inclusion/Exclusion criteria number	Check
PDEV29	Estimated glomerular filtration rate by the 4-variable Modification of Diet in Renal Disease of < 45 mL/min/1.73 m ²	Yes	Yes	Eligibility and Entry Criteria	Exclusion criteria #18	If identified by medical review or corresponding exclusion criterion is ticked Yes.
PDEV30	TSH < 0.01 or ≥ 7.1 mIU/L at Screening	Yes	Yes	Eligibility and Entry Criteria	Exclusion criteria #19	If identified by medical review or corresponding exclusion criterion is ticked Yes.
PDEV31	Clinically significant laboratory abnormality	Yes	Yes	Eligibility and Entry Criteria	Exclusion criteria #20	If identified by medical review or corresponding exclusion criterion is ticked Yes.
PDEV32	B cell (CD19) count < 50% of the lower limit of normal	Yes	Yes	Eligibility and Entry Criteria	Exclusion criteria #21	If identified by medical review or corresponding exclusion criterion is ticked Yes.
PDEV33	Significant cytopenia	Yes	Yes	Eligibility and Entry Criteria	Exclusion criteria #22	If identified by medical review or corresponding exclusion criterion is ticked Yes.
PDEV34	Participation in any investigational drug trial	Yes	Yes	Eligibility and Entry Criteria	Exclusion criteria #23	If identified by medical review or corresponding exclusion criterion is ticked Yes.

Protocol Deviation number	Protocol Deviation	Important	Clinically Important	Type criteria	Inclusion/Exclusion criteria number	Check
PDEV35	Subjects receiving medications, herbal supplements, or food known to be moderate or strong inhibitors of CYP3A or drugs mainly metabolized by CYP3A (see Section 6.5.2 of CTP)	Yes	Yes	Eligibility and Entry Criteria	Exclusion criteria #24	If identified by medical review or corresponding exclusion criterion is ticked Yes.
PDEV36	Concurrent treatment with a non-permitted drug or procedure (refer to section 6.5.2 of CTP).	Yes	case by case basis			If identified by medical review.
PDEV37	Incorrect treatment group IP dispensed to subject	Yes	case by case basis	IP Compliance		If randomized treatment is different from actual treatment
PDEV38	Non-compliant with IP usage	Yes	case by case basis	IP Compliance		Check if <80% of >120%
PDEV39	IP not taken in compliance with protocol eg, at the appropriate times, during/timed with meals/snacks	case by case basis	case by case basis	IP Compliance		From monitoring log/Medical Review
PDEV40	Subject did not sign ICF and was enrolled	Yes	Yes	Informed Consent Criteria		ICF date is greater than randomization date

Protocol Deviation number	Protocol Deviation	Important	Clinically Important	Type criteria	Inclusion/Exclusion criteria number	Check
PDEV41	Subject used prohibited medication(s)	case by case basis	case by case basis	Other Criteria		Medical review
PDEV42	Lab safety and/or PK samples not drawn according to protocol requirements	case by case basis	case by case basis	Laboratory Assessment Criteria		Monitoring deviation log, Medical review

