5.3.1 Inclusion Criteria

The current trial will enroll subjects who fulfill the following:

1. Men or women 18 to 75 years of age at the time of informed consent signature
2. Confirmed diagnosis of RA according to 2010 American College of Rheumatology (ACR)/The European League Against Rheumatism (EULAR) RA classification criteria of at least 6 months duration

CCI

CONFIDENTIAL
INFORMATION

30/106

3. Positive RF and/or anti-CCP
4. Persistently active disease defined as ≥ 6 swollen joints (of 66 counted) and ≥ 6 tender joints (of 68 counted)
5. hsCRP ≥ 3.6 mg/L
6. Treatment for ≥ 12 weeks with 10 to 25 mg/week MTX at a stable dose for at least 4 weeks prior to dosing with the IMP and maintained throughout the trial
7. Women of childbearing potential must use a highly effective method of contraception combined with one supplementary barrier method for 4 weeks prior to randomization, throughout the trial, and for 90 days after the last dose of IMP. For the purposes of this trial:
 - Females who are postmenopausal (age-related amenorrhea ≥ 12 consecutive months and increased follicle-stimulating hormone [FSH] > 40 mIU/mL), or who have undergone hysterectomy or bilateral oophorectomy are exempt from pregnancy testing. If necessary to confirm postmenopausal status, an FSH will be drawn at Screening
 - The definition of highly effective contraception includes:
 - combined (estrogen and progestogen containing) hormonal contraception associated with inhibition of ovulation; oral, intravaginal or transdermal
 - progestogen-only hormonal contraception associated with inhibition of ovulation; oral, injectable or implantable
 - intrauterine device (IUD)
 - intrauterine hormone-releasing system (IUS)
 - bilateral tubal occlusion
 - vasectomized partner
 - sexual abstinence
 - Supplementary barrier methods include:
 - male or female condom with or without spermicide
 - cap, diaphragm or sponge with spermicide
8. Men must agree to use and to have their female partners use a highly effective method of contraception combined with one supplementary barrier method as defined above for at least 90 days after the last IMP administration.
9. Women of childbearing potential must have a negative serum pregnancy test at the Screening Visit and a negative urine pregnancy test at Day 1/randomization before dosing

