9.2 Subject Information and Informed Consent

An unconditional prerequisite for each subject prior to participation in the trial is written informed consent, which must be given before any trial-related activities are carried out. Adequate information must therefore be given to the subject by the Investigator or an appropriate designee (if local regulations permit) before informed consent is obtained.

A Subject Information Sheet must be prepared in the local language in accordance with the ICH GCP guidelines and will be provided by the Sponsor for the purpose of obtaining informed consent. In addition to providing this written information to a potential subject, the Investigator or a designate will inform the subject verbally of all pertinent aspects of the trial, using language chosen so that the information can be fully and readily understood by laypersons. The subject will be given sufficient time to read the information and the opportunity to ask questions and to request additional information and clarification.

If permitted by national regulations, a person other than the Investigator may inform the subject about the trial and sign the Informed Consent Form, as above.

After the information is provided by the Investigator, the Informed Consent Form must be signed and dated by the subject and the Investigator.

The signed and dated declaration of informed consent will remain at the Investigator’s site, and must be safely archived so that the forms can be retrieved at any time for monitoring, auditing, and

inspection purposes. A copy of the signed and dated information and Informed Consent Form should be provided to the subject prior to participation.

Whenever important new information becomes available that may be relevant to informed consent, the Investigator will revise the Subject Information Sheet and any other written information to be provided to the subjects and submit them to the IRB for review and opinion. Using the approved revised Subject Information Sheet and other written information, the Investigator will explain the changes to the previous version to each trial subject and obtain new written consent for continued participation in the trial. The subject will be given sufficient time to read the information and the opportunity to ask questions and to request additional information and clarification about the changes.

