13.1 Demographics

- Demographic characteristics
 - Sex: male, female
 - Race: White, Black or African American, Asian, American Indian or Alaska Native, Native Hawaiian or Other Pacific Islander, Other
 - Ethnicity: Hispanic or Latino, Not Hispanic or Latino
 - Age (years) at informed consent: summary statistics
 - Age categories :
 - < 65 years, ≥ 65 years
- Geographic Region (eg Europe, North America)
- European Economic Area (Yes/No)

Specifications for computation:

- Age (years):

- $(\text{date of given informed consent} - \text{date of birth} + 1) / 365.25$
- In case of missing day for at least one date, but month and year available for both dates:
For the derivation of age, the day of informed consent and the day of birth will be set to 1 and the formula above will be used
- In case of missing month for at least one date, but year available for both dates:
For the derivation of age, the day and the month of informed consent and the day and month of birth will be set to 1 and the formula above will be used
- Site codes will be used for the determination of the subject's geographic region and European Economic Area membership.

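### PDEV01 flags every eligible 75-year-old, and the programmed part of PDEV06 neither derives the 4-week stable methotrexate dose nor says how several dose records are combined

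*SAP*

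**What the plan says.** **Age.** Protocol 5.3.1, criterion 1, admits "Men or women 18 to 75 years of age at the time of informed consent signature". The check, PDEV01 in SAP Appendix 3 (Section 19.3), reads: "If calculated age at informed consent is <18 or >75 years, or if corresponding inclusion criterion is ticked No". SAP 13.1 calculates age as (date of consent − date of birth + 1)/365.25. It states no truncation or rounding. If a day is missing, "the day of informed consent and the day of birth will be set to 1 and the formula above will be used"; if a month is missing, day and month are both set to 1.

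**Methotrexate.** Protocol 5.3.1, criterion 6, asks for at least 12 weeks of treatment at 10 to 25 mg/week, with "MTX at a stable dose for at least 4 weeks prior to dosing with the IMP and maintained throughout the trial". PDEV06 fires if no relevant methotrexate record exists, or for "a relevant medication reported with a duration less than 12 weeks or a dose not included between 10 and 25 mg", or if the site ticked No for criterion 6.

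**Status and use.** Appendix 3 marks both checks as important and clinically important. SAP 10.1 applies the second label to deviations that lead to exclusion from an analysis set. It also says that no per-protocol analysis is planned, that deviations may come from monitoring, medical review or programming, and that they are confirmed at or before the Data Review Meeting. SAP 12.2 tabulates and lists them.

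**The concern.** A programmed check should reproduce the criterion that it names. PDEV01 compares a decimal age with a limit written in whole years, so it appears to reject a full year of age that the protocol admits. A correct Yes from the site does not clear the flag, because the two conditions are joined by *or*.

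PDEV06 covers only the first half of criterion 6. The stable dose before dosing is the other half, and the trial's title refers to it. Nothing in the derivation compares the last methotrexate dose change with the first IMP date. Dose changes are the situation in which a subject has more than one record, and the check is silent on whether records are tested singly or together.

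At stake is whether the deviation tables and listings in the study report describe the enrolled population correctly, and whether the Data Review Meeting receives the right cases. With about 64 subjects randomized, each wrong flag is 1/64 = 1.6% of the trial.

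**Working it through.** The plan gives no figure for these checks, so there is none to reproduce. The working applies the written rules.

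**PDEV01**

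Inputs: the SAP 13.1 formula, the flag at >75, and criterion 1. Assumption: consent dates from 1 June 2016 to 31 March 2017, around the planned trial period.

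1. The limit in days is 75 × 365.25 = 27,393.75.
2. For these consent dates, 75 calendar years span 75 × 365 + 19 leap days = 27,394 days.
3. On the 75th birthday: (27,394 + 1)/365.25 = 75.003, flagged.
4. The day before, still aged 74: (27,393 + 1)/365.25 = 75.0007, flagged.
5. Born 1 June 1941, consent 1 September 2016: (27,394 + 92 + 1)/365.25 = 75.255, flagged.
6. Every consent date crossed with every birth date giving calendar age 75 makes 304 × 365 = 110,960 pairs. All 110,960 are flagged. Among pairs with calendar age 74, 304 are flagged, all on the day before the 75th birthday.
7. Birth month missing: a year difference of 75 gives 75.001 (1941 to 2016) or 75.003 (1942 to 2017). Both are flagged, whether or not the birthday has passed.
8. At the lower limit, none of the 110,960 pairs with calendar age 18 is flagged.
9. Counting completed years by birthday leaves no 75-year-old flagged. Truncating the SAP 13.1 value is not quite equivalent. The day before the 76th birthday gives (76 × 365 + 19 − 1 + 1)/365.25 = 27,759/365.25 = 76.000, which truncates to 76.

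**PDEV06**

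Inputs: criterion 6 and the programmed wording. The histories are illustrative, with durations counted to first IMP (PDEV06 does not state the end point). *Separate* tests each record alone; *summed* adds the weeks of in-range records.

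| Methotrexate history (weekly dose × weeks) | Meets criterion 6 | Separate | Summed |
|---|---|---|---|
| 20 mg × 32 | yes | no flag | no flag |
| 15 mg × 26, then 20 mg × 6 | yes | **flag** | no flag |
| 15 mg × 20, then 20 mg × 8 | yes | **flag** | no flag |
| 7.5 mg × 8, then 15 mg × 30 | yes | **flag** | no flag |
| 15 mg × 20, then 20 mg × 13 | yes | no flag | no flag |
| 15 mg × 20, then 20 mg × 2 | no | flag | **no flag** |

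Bold marks a wrong result. Tested separately, the 6-week and 2-week cases get the same flag, so eligible and ineligible subjects cannot be told apart. Summed, the wrong flags disappear, but so does the only signal of the 2-week change. Neither reading implements criterion 6.

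**The case against.** **A backstop exists.** The tick-box route in PDEV06 refers to the whole of criterion 6, including stability, and SAP 10.1 adds monitoring and medical review. This stands. A reader might infer that stability is never checked; the documents do not support that. What is missing is a derivation from the medication data. The tick-box repeats the site's own judgement, and PDEV06, unlike PDEV10 and PDEV12 to PDEV35, does not name medical review as a source.

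**The two PDEV06 faults need opposite readings.** This also stands. Wrong flags arise only if a dose change opens a new eCRF record and records are tested one by one. Protocol 6.5 requires changes to be recorded but does not show the layout. The word *relevant* could also exclude an old titration record. The defect is that the SAP does not choose a reading and neither one works.

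**The upper age limit might mean the exact 75th birthday.** That is not how age in years is normally read. Even so, PDEV01 would still wrongly flag a subject the day before that birthday.

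**The analysis is untouched.** Largely right. A reader might infer from the clinically important label that flagged subjects leave the efficacy analysis. SAP 10.1 attaches that label to exclusions but creates no exclusion rule. The mITT set and SAF have no eligibility condition, there is no per-protocol set, and the Data Review Meeting can remove wrong flags. For PK and PD, the examples in SAP 12.2.2 include concomitant-medication violations but neither age nor methotrexate history, so an effect there is only possible.

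**Conclusion.** PDEV01 is wrong as written. Applied with the SAP 13.1 formula, it labels every eligible 75-year-old, and a subject one day short of 75, as an important and clinically important eligibility deviation. This rests only on the formula being used without truncation, which is what the SAP states.

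PDEV06 is incomplete. Its programmed part does not derive the 4-week stability requirement, does not say how several methotrexate records are combined, and omits the weekly unit from the dose limit. Which error follows depends on a record layout and a reading that the documents do not give.

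The consequence is wrong deviation tables and listings and possibly wrong PK/PD set decisions. The primary mITT ACR20 result does not change. The number of subjects affected is not in the documents.

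Two further inferences are not supported:

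- *Unstable methotrexate before baseline explains the ACR20 difference.* The comparison is between randomized, blinded arms, so such changes are balanced in expectation, and a deviation flag would not adjust for them.
- *PDEV40 needs the same repair.* It tests whether "ICF date is greater than randomization date", while Protocol 9.2 asks for "written informed consent, which must be given before any trial-related activities are carried out". Its label, however, concerns enrolment without consent, and PDEV11 covers a missing consent date. Protocol 5.3 and Section 7 exempt routine care, and an existing chest X-ray is accepted. Comparing consent with the first screening procedure could therefore flag permitted cases. Any such check should be limited to trial-specific, non-routine procedures.

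**What to change.** **PDEV01.** Use age in completed years at consent, and flag below 18 or at 76 and above. Count years by birthday rather than truncating the SAP 13.1 decimal, which reaches 76 a day early. Where the birth day or month is missing and the result is at the boundary, refer the case to medical review.

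**PDEV06.** Test duration over consecutive methotrexate records up to first IMP, at least 12 weeks at 10 to 25 mg/week, with the weekly unit stated. Add a separate flag when the last methotrexate dose change is less than 28 days before first IMP. SAP Section 11 generally does not impute missing dates, so send incomplete dates to medical review.

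**Result.** On the cases above, the 75-year-olds are no longer flagged, 15 mg × 26 weeks then 20 mg × 6 weeks is cleared, and 15 mg × 20 weeks then 20 mg × 2 weeks is flagged.

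**Cost.** Changed wording in Appendix 3 and a few program lines on dates and doses already collected, plus medical review time for incomplete dates. It should be in place before the Data Review Meeting.
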